19.1.4 Early Induction Termination

Table 24: Summary of Early Induction Terminations by Site

	Gibson Recovery Center (N=XX)	Nexus Recovery Center (N=XX)	Stony Brook Eastern Long Island Hospital (N=XX)	Aspire Health Partners (N=XX)	Avery Road Treatment Center (N=XX)	ADAPT (N=XX)	Total (N=XX)
Number of early induction terminations	N (X.x%)						
Reason for early induction termination ¹							
Prefers other medication (buprenorphine or methadone)	N (X.x%)						
Prefers to not be on medication for opioid use disorder							
Does not want naltrexone since it blocks opioids and prevents high							
Fear of precipitated withdrawal from naltrexone shot							
Withdrawal symptoms were too uncomfortable							
Left detox unit early							
Medical contraindication (including pregnancy, COVID-19 infection)							
Psychiatric contraindication							
Other							
Unknown							

¹ Percentage was based on the number of early induction terminations and may exceed 100% if multiple reasons were selected.

Table 25: Summary of Early Induction Terminations by Induction Procedure			
	Induction Procedure		
	Standard (N=XX)	Rapid (N=XX)	Total (N=XX)
Number of early induction terminations	N (X.x%)		
Reason for early induction termination ¹			
Prefers other medication (buprenorphine or methadone)	N (X.x%)		
Prefers to not be on medication for opioid use disorder			
Does not want naltrexone since it blocks opioids and prevents high			
Fear of precipitated withdrawal from naltrexone shot			
Withdrawal symptoms were too uncomfortable			
Left detox unit early			
Medical contraindication (including pregnancy, COVID-19 infection)			
Psychiatric contraindication			
Other			
Unknown			

¹Percentage was based on the number of early induction terminations and may exceed 100% if multiple reasons were selected.

19.1.5 Treatment Exposure

Table 26: Summary of Treatment Exposure by Site					
Site	Number Enrolled	Participants with First Injection Administered While on the Unit¹	Participants with Second Injection Administered²	Participants with Third Injection Administered³	Treatment Exposure Percentage⁴
Gibson Recovery Center	N	N (X.x%)	N (X.x%)	N (X.x%)	N (X.x%)
Nexus Recovery Center					
Stony Brook Eastern Long Island Hospital					
Aspire Health Partners					
Avery Road Treatment Center					
ADAPT					
Total					

¹ Percentage was calculated as the number who had first injection administered while on the unit out of the total number enrolled.

² Percentage was calculated as the number who had second injections administered out of total number who received the first injection while on the unit.

³ Percentage was calculated as the number who had third injections administered out of total number who received the second injection.

⁴ Percentage was calculated as the number of injections administered out of the expected three injections for participants who received the first injection while on the unit.

Table 27: Summary of Treatment Exposure by Induction Procedure					
Induction Procedure	Number Enrolled	Participants with First Injection Administered While on the Unit ¹	Participants with Second Injection Administered ²	Participants with Third Injection Administered ³	Treatment Exposure Percentage ⁴
Standard	N	N (X.x%)	N (X.x%)	N (X.x%)	N (X.x%)
Rapid					
Total					

¹ Percentage was calculated as the number who had first injection administered while on the unit out of the total number enrolled.

² Percentage was calculated as the number who had second injections administered out of total number who received the first injection while on the unit.

³ Percentage was calculated as the number who had third injections administered out of total number who received the second injection.

⁴ Percentage was calculated as the number of injections administered out of the expected three injections for participants who received the first injection while on the unit.

Table 28: Summary of XR-NTX Injections in Induction Failure Participants by Site			
Site	Number Enrolled	Number of Induction Failures ¹	Induction Failures Who Had At Least One XR-NTX Injection Administered During Post-Induction Phase ²
Gibson Recovery Center	N	N (X.x%)	N (X.x%)
Nexus Recovery Center			
Stony Brook Eastern Long Island Hospital			
Aspire Health Partners			
Avery Road Treatment Center			
ADAPT			
Total			

¹ Percentage was calculated as the number who did not have first injection while on the unit administered out of the total number enrolled.

² Percentage was calculated as the number who had injections administered out of total number of induction failures.

Table 29: Summary of XR-NTX Injections in Induction Failure Participants by Induction Procedure			
Induction Procedure	Number Enrolled	Number of Induction Failures¹	Induction Failures Who Had at Least One XR-NTX Injection Administered During Post-Induction Phase²
Standard	N	N (X.x%)	N (X.x%)
Rapid			
Total			

¹ Percentage was calculated as the number who did not have first injection while on the unit administered out of the total number enrolled.

² Percentage was calculated as the number who had injections administered out of total number of induction failures.

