2.1.2 Secondary Objectives

The key secondary objective is to summarize the below outcome to confirm expected characteristics of the RP compared to SP:

1. Time to receipt of first injection of XR-NTX from day of admission for participants that receive first injection of XR-NTX while on the unit.

Additional key secondary objectives are to compare the below outcomes of RP versus SP for all enrolled participants, intent-to-treat (ITT) population.

2. Craving for opioids measured by Visual Analog Scales (VAS).
3. Opioid withdrawal symptoms as measured by the Subjective Opioid Withdrawal Scale (SOWS) and the Clinical Opiate Withdrawal Scale (COWS).
4. Safety, as measured by overdose questionnaire, targeted safety events and serious adverse events.

Other secondary objectives are to compare the below outcomes of RP vs. SP for participants who receive the first injection while on the unit.

5. Retention in the trial to receive the second and the third XR-NTX injections.
6. Craving for opioids measured by Visual Analog Scales.
7. Opioid withdrawal symptoms following XR-NTX injection as measured by the Subjective Opioid Withdrawal Scale.
8. Safety, as measured by overdose questionnaire, targeted safety events and serious adverse events.
9. Opioid abstinence, as measured by the Timeline Followback (TLFB) (self-report days using opioids) and proportion of opioid-positive urine tests (UDS).

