8.4 Definition of the Secondary Outcome Measures

Key secondary analyses to be conducted by the DSC:

A key secondary objective is to summarize the below outcome to confirm expected characteristics of the RP compared to SP:

1. The time to receipt of first injection of XR-NTX as measured by the number of days from admission to first XR-NTX injection. This will be conducted on the successfully inducted population only. Day of admission is defined as Day 1 (E97ADMDT) as recorded on the ENRC or ENRD forms, and day of first XR-NTX injection (EOIINJDT) is captured on the End of Induction form (EOI). It will be calculated as Date of injection (EOI.EOIINJDT) – Date of admission (ENRC/ENRD.E97ADMDT) +1.

Additional key secondary objectives are to compare the below outcomes of RP versus SP for all enrolled participants (ITT population).

2. Craving for opioids measured by Visual Analog Scales (VAS) as captured daily on the self-reported inpatient opioid craving form (OCI) during induction phase. The OCI form collects intensity of craving both at time of assessment and within the last 24 hours prior to assessment. If either measurement is collected multiple times on the same assessment date, the average measurement will be used for analysis.
3. Opioid withdrawal symptoms as measured by the Subjective Opioid Withdrawal Scale (SOWS) and the Clinical Opiate Withdrawal Scale (COWS). SOWS is captured on the SBW form at baseline and daily during induction phase. COWS is captured on the COW

form starting with day of admission and daily during the induction phase leading to the first XR-NTX injection. Note that during induction, COWS may be measured multiple times per day while SOWS is expected to be assessed only once per day. If multiple SOWS measures are collected on the same assessment date, the average measurement will be used for analysis. If multiple COWS measures are collected on the same assessment, the peak measurement will be used.

4. Retention in the trial to receive at least one XR-NTX injection after the first injection as captured on the XR-NTX Administration (INN) form.
5. Safety, as measured by targeted safety events, overdoses, and serious adverse events related to study medication during the induction phase and during eight weeks of post-induction. Detail on safety outcome analysis is provided in Section 9.0.

Other secondary analyses to be conducted by LN:

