Targeted safety events, overdoses and SAEs, related to study medications	Frequency of targeted safety events, overdose episodes and SAEs by relationship to study medication during the induction period and during eight weeks of post-induction treatment	RP and SP will produce equivalent rates of targeted safety events and SAEs during the induction and during the first eight weeks of treatment with XR-NTX. Significance/Rationale: Careful documentation of SAEs, targeted safety events, and overdose episodes, would be considered essential safety data, and important component of a comparative effectiveness trial.
Receive second and third injections (binary: did or did not receive second and third dose of XR-NTX)	Proportion of participants that receive second and third injection of XR-NTX (at 4 weeks and 8 weeks, from first injection)	Participants in RP and SP will have comparable rates of treatment retention. Significance/Rationale: Because there is no difference in tolerability of the first and second XR-NTX injections in both study arms, we do not expect differential treatment dropout.
Use of opioids over time during the 8-week of post-induction treatment while on study medication (Weekly TLFB, confirmed by urine drug screens when available)	Percent of participants positive for opioids using weekly TLFB during eight weeks of post-induction, and urine drug screens at week 4 and 8.	RP and SP will produce comparable levels of opioid use. Significance/Rationale: XR-NTX produces complete blockade of opioid effects, so that during treatment with monthly injections, opioid use can be expected to be minimal and no different between study arms.

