Gibson Recovery Center versus ADAPT								
Stony Brook Eastern Long Island Hospital versus ADAPT								

Table 49: Retention in the Study to Receive at Least One XR-NTX Injection after Induction Success

Induction Procedure	Number with Induction Success	At Least One Additional Injection Administered	Results			
			Odds Ratio	95% Lower Confidence Limit	95% Upper Confidence Limit	p-value
Rapid	N (X.x%)	N (X.x%)	X.xx	X.xx	X.xx	0.xxx
Standard						
Total						

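### The only third-injection percentage in the listed Data and Statistics Center (DSC) tables is conditional on the second injection, so it is not the retention proportion the SAP sets among inducted participants

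*SAP*

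**What the plan says.** SAP 2.1.2 lists as objective 5 "Retention in the trial to receive the second and the third XR-NTX injections". The sentence that introduces it fixes the group: "Other secondary objectives are to compare the below outcomes of RP vs. SP for participants who receive the first injection while on the unit". SAP 3.1.5 names that group the inducted population. Table 5 in SAP 8.4 gives the measure as "Proportion of participants that receive second and third injection of XR-NTX (at 4 weeks and 8 weeks, from first injection"), with the hypothesis that the Rapid Procedure (RP) and the Standard Procedure (SP) have comparable retention.

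The retention outcome that the DSC will model is narrower. SAP 8.4 item 4 reads "Retention in the trial to receive at least one XR-NTX injection after the first injection as captured on the XR-NTX Administration (INN) form". SAP 8.5 models it like the primary outcome, and the shell is Table 49, "Retention in the Study to Receive at Least One XR-NTX Injection after Induction Success".

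The third injection has its own column in the treatment exposure shells, Tables 26 (by site) and 27 (by induction procedure) in SAP 19.1.5. The footnotes set these bases:

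- Footnote 1: first injection on the unit, out of all enrolled.
- Footnote 2: "Percentage was calculated as the number who had second injections administered out of total number who received the first injection while on the unit".
- Footnote 3: "Percentage was calculated as the number who had third injections administered out of total number who received the second injection".
- Footnote 4 (exposure): "number of injections administered out of the expected three injections for participants who received the first injection while on the unit".

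**The concern.** Objective 5 and Table 5 concern receipt of the second and third injections in the inducted population. Neither makes the third injection conditional on the second. Footnote 3 does, so participants lost before the second injection leave the denominator before the Week 8 percentage is formed.

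That loss matters to the trial. Protocol 4.1.5 treats acceptance of the second and third injections as an important outcome that may reflect how well the first injection and the induction were tolerated. Protocol 10.7 says the third injection is given so that retention eight weeks after induction can be assessed objectively. A tolerability problem with one procedure could show first as loss before the second injection, and those who remain may be a more adherent group.

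No other listed output supplies the figure. Table 49 covers at least one further injection. The list of Lead Node analyses in SAP 8.4 does not name third-injection retention. No DSC shell prints third/first.

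**Working it through.** The shells are empty, so there is no figure of the plan's to reproduce.

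**Notation.** Let n1, n2 and n3 be the numbers given the first injection on the unit, the second and the third, and assume that everyone with a third injection also had a second. Let a = n2/n1 (footnote 2) and b = n3/n2 (footnote 3).

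- Third/first = n3/n1 = a × b.
- Overstatement if b is read as retention: b ÷ (a × b) = 1/a = n1/n2. This equals 1 only if every inducted participant receives the second injection.
- Exposure (footnote 4) = (n1 + n2 + n3)/(3 × n1) = (1 + a + ab)/3.

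**Simplest case (assumed).** With a = b = 0.70, the cell prints 70%; third/first is 0.70 × 0.70 = 49%.

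**Scaled to the trial.** Protocol 8.0 plans about 225 participants per procedure, and SAP 12.0 assumes induction success of 0.55 (SP) and 0.70 (RP). This gives 225 × 0.55 = 123.75, about 124 inducted in SP, and 225 × 0.70 = 157.5, about 158 in RP. The second- and third-injection counts below are assumed.

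| Example | Procedure | n1 → n2 → n3 | Second/first | Third/second (footnote 3) | Third/first | Exposure |
|---|---|---|---|---|---|---|
| A | SP | 124 → 62 → 56 | 50.0% | 90.3% | 45.2% | 65.1% |
| A | RP | 158 → 111 → 89 | 70.3% | 80.2% | 56.3% | 75.5% |
| B | SP | 124 → 81 → 65 | 65.3% | 80.2% | 52.4% | 72.6% |
| B | RP | 158 → 95 → 80 | 60.1% | 84.2% | 50.6% | 70.3% |

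In A, footnote 3 favours SP and third/first favours RP. The overstatement factors are 124/62 = 2.0 (SP) and 158/111 = 1.4 (RP). In B, footnote 3 favours RP and third/first favours SP, with smaller differences between the procedures.

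**When the order reverses.** The procedures must differ on a in the opposite direction to b, and by enough to outweigh it. With equal a the order cannot change. Over a grid of a and b from 30% to 95% in 5-point steps, the order reverses in 8,146 of 35,402 non-tied combinations (23%). With rates of 50% to 90% and differences of at most 10 points, it reverses in 210 of 1,140 (18%). These are shares of a grid, not probabilities.

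**What the rest of the row shows.** Suppose b is higher in RP but ab is higher in SP. Then a must be higher in SP, and so (1 + a + ab)/3 is higher in SP as well. In every reversal, the second-injection and exposure percentages therefore give the same order as third/first, as in A and B.

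**The case against.** The tables are titled treatment exposure and no passage says that the footnote 3 column estimates retention. Footnotes 1 to 3 form an ordinary step-by-step cascade, each column divided by the one before it, with every base stated. The counts sit side by side, so third/first is one division. No test or model uses the column. All of this stands, and it limits the point to presentation.

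A reader might infer that the tables would mislead about which procedure retains participants better. The documents do not support that. It applies to one cell read alone, two other percentages in the same row correct it, and every injection rate behind it is assumed.

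A reader might also take the closing words of the Table 5 measure, about the first injection, as naming a denominator. They describe timing; the base comes from SAP 2.1.2 and 3.1.5.

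Finally, SAP Table 1 assigns other secondary outcomes to the Lead Node, and SAP 18.0 lists DSC output only. Absence from the DSC shells does not prove that third/first will go unreported. But the list of Lead Node analyses in SAP 8.4 does not name it, so no planned output visibly delivers it.

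**Conclusion.** The point holds as a mismatch between a stated secondary measure and the only listed third-injection percentage. The cell exceeds third/first by n1/n2 whenever any inducted participant misses the second injection. The size cannot be fixed from the documents: in the assumed examples the factor runs from 1.4 (A, RP) to 2.0 (A, SP). A change of order is possible but needs opposite differences at the two stages, and the rest of the row would expose it.

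The arithmetic assumes that third-injection recipients are a subset of second-injection recipients. The shells do not say how to count someone who misses the second injection and is injected at Week 8. The primary analysis and the retention model behind Table 49 are unaffected.

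**What to change.** In Tables 26 and 27, print the third-injection percentage out of participants with the first injection on the unit, the group that footnotes 2 and 4 already use. Keep third/second only in a column labelled as conditional on the second injection.

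A percentage over all enrolled is not required. Protocol 16.3.2 does mention analysing post-injection outcomes in all enrolled participants, but the SAP restricts this objective to the inducted population and reports injections in induction failures separately (SAP 7.0, Tables 28 and 29).

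The cost is one footnote and one denominator, or one extra column. No new data are needed. The printed third-injection percentage will be lower than under footnote 3 unless everyone inducted has the second injection.

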19.1.6 Primary Outcome Analyses

Table 30: Summary of Primary Outcome by Site		
Site	Number Enrolled	First Injection Administered While on the Unit
Gibson Recovery Center	N	N (X.x%)
Nexus Recovery Center		
Stony Brook Eastern Long Island Hospital		
Aspire Health Partners		
Avery Road Treatment Center		
ADAPT		
Total		

Table 31: Summary of Primary Outcome by Step		
Step	Number Enrolled	First Injection Administered While on the Unit
Step 1	N	N (X.x%)
Step 2		
Step 3		
Step 4		
Step 5		
Total		

Table 32: Summary of Primary Outcome and Days to Induction¹ by Site and Step

			Step					Induction Procedure		Total	
			Step 1	Step 2	Step 3	Step 4	Step 5	Standard	Rapid		
Site	Gibson Recovery Center	Percent inducted	n/N (X.x%)					-			
		Average days to induction (SD)	X.x (X.xx)					-			
	Nexus Recovery Center	Percent inducted									
		Average days to induction (SD)									
	Stony Brook Eastern Long Island Hospital	Percent inducted									
		Average days to induction (SD)									
	Aspire Health Partners	Percent inducted									
		Average days to induction (SD)									
	Avery Road Treatment Center	Percent inducted									
		Average days to induction (SD)									
	ADAPT	Percent inducted							-		
		Average days to induction (SD)							-		
Induction Procedure	Standard Total	Percent inducted							-	-	
		Average days to induction (SD)							-	-	
	Rapid Total	Percent inducted						-		-	
		Average days to induction (SD)						-		-	
Total		Percent inducted						-	-		
		Average days to induction (SD)						-	-		

Table 33: Summary of Primary Outcome by Induction Procedure							
Induction Procedure	Number Enrolled	First Injection Administered While on the Unit	Results ¹				
			Odds Ratio	95% Lower Confidence Limit	95% Upper Confidence Limit	p-value	Number Needed to Treat
Rapid	N	N (X.x%)	X.xx	X.xx	X.xx	0.xxx	X.x
Standard							
Total							

¹ Results are obtained from the generalized linear mixed effects model. To show Rapid Procedure is non-inferior to Standard Procedure, the lower bound of the two-sided 95% CI for the odds ratio for Rapid versus Standard Procedure needs to be higher than 0.67. If the 95% confidence interval for odds ratio lies entirely above 0.67 and also above 1, then there is evidence of superiority in terms of statistical significance at the 5% level (p < 0.05).

19.1.7 Supportive Analyses of Primary Outcome

Table 34: Summary of Primary Outcome by Sex and Induction Procedure								
	Standard Procedure		Rapid Procedure		Results ¹			
Subgroup	Number Enrolled	First Injection Administered While on the Unit	Number Enrolled	First Injection Administered While on the Unit	Odds Ratio	95% Lower Confidence Limit	95% Upper Confidence Limit	p-value
Male	N	X (X.x%)	N	X (X.x%)	X.xx	X.xx	X.xx	0.xxx
Female								

¹ Results are obtained from the generalized linear mixed effects model. The p-value for the interaction term between induction procedure and subgroup is shown.

Table 35: Summary of Primary Outcome by Age and induction Procedure

Subgroup	Standard Procedure		Rapid Procedure		Results ¹			
	Number Enrolled	First Injection Administered While on the Unit	Number Enrolled	First Injection Administered While on the Unit	Odds Ratio	95% Lower Confidence Limit	95% Upper Confidence Limit	p-value
≤ 25 years	N	X (X.x%)	N	X (X.x%)	X.xx	X.xx	X.xx	0.xxx
> 25 years								

¹Results are obtained from the generalized linear mixed effects model. The p-value from the interaction between induction procedure and subgroup is shown.

Table 36: Summary of Primary Outcome by Race and Induction Procedure

Subgroup	Standard Procedure		Rapid Procedure		Results ¹			
	Number Enrolled	First Injection Administered While on the Unit	Number Enrolled	First Injection Administered While on the Unit	Odds Ratio	95% Lower Confidence Limit	95% Upper Confidence Limit	p-value
Black	N	X (X.x%)	N	X (X.x%)	X.xx	X.xx	X.xx	0.xxx
White								
Other								

¹Results are obtained from the generalized linear mixed effects model. The p-value for the interaction term between induction procedure and subgroup is shown.

Table 37: Summary of Primary Outcome by Ethnicity and Induction Procedure

Subgroup	Standard Procedure		Rapid Procedure		Results¹			
	Number Enrolled	First Injection Administered While on the Unit	Number Enrolled	First Injection Administered While on the Unit	Odds Ratio	95% Lower Confidence Limit	95% Upper Confidence Limit	p-value
Not Hispanic or Latino	N	X (X.x%)	N	X (X.x%)	X.xx	X.xx	X.xx	0.xxx
Hispanic or Latino								

¹Results are obtained from the generalized linear mixed effects model. The p-value for the interaction term between induction procedure and subgroup is shown.

[figure not shown]

Figure 9: Forest Plot of Odds Ratios by Sub-groups

Example figure provided.

Table 38: Summary of Primary Outcome Excluding Participants Admitted More than Four Calendar Days Prior to Enrollment by Induction Procedure						
Induction Procedure	Number Admitted within Four Calendar Days Prior to Enrollment	First Injection Administered While on the Unit	Odds Ratio	95% Lower Confidence Limit	95% Upper Confidence Limit	p-value
Rapid	N	N (X.x%)	X.xx	X.xx	X.xx	0.xxx
Standard						
Total						

Participants admitted more than four calendar days prior to enrollment (N=6) were excluded to reflect the updated study exclusion criteria in amended protocol version 3.0 per DSMB recommendation.

Table 39: Summary of Primary Outcome Excluding Participants Enrolled During Pre-Implementation Phase by Induction Procedure

Induction Procedure	Number Admitted Outside of the Pre-implementation Phase	First Injection Administered While on the Unit	Odds Ratio	95% Lower Confidence Limit	95% Upper Confidence Limit	p-value
Rapid	N	N (X.x%)	X.xx	X.xx	X.xx	0.xxx
Standard						
Total						

Participants enrolled in Standard Procedure in the 8 weeks prior to the site crossing over to Rapid Procedure (N=32) were excluded to account for any possible contamination of the SP arm with the RP training.

Table 40: Summary of Primary Outcome by Presence of Baseline Fentanyl Use

Fentanyl Use at Baseline	Number with Baseline Urine Drug Screen	First Injection Administered While on the Unit	Odds Ratio	95% Lower Confidence Limit	95% Upper Confidence Limit	p-value
Positive	N	N (X.x%)	X.xx	X.xx	X.xx	0.xxx
Negative						
Total						

Table 41: Summary of Primary Outcome by Induction Procedure in Participants Who Initiated Buprenorphine

Induction Procedure	Number Enrolled	Participants who Initiated Buprenorphine ¹	Participants who Received First XR-NTX Injection ²
Rapid	N	N (X.x%)	N (X.x%)
Standard			
Total			

¹ Percentage was calculated with the denominator as number enrolled.

² Percentage was calculated with the denominator as the number who initiated buprenorphine.

